
## 10.0 DATA COLLECTION AND MONITORING

## 10.1 Record Keeping

All clinical data will be recorded onto standardized case record forms (CRFs) by study physicians. Laboratory data will be recorded in a laboratory record book by the study laboratory technologists and then transferred to the case record forms by study coordinators, who will review the case record forms frequently for completeness and accuracy. Data will be entered directly from CRFs into a computerized database or transferred from the CRFs onto standardized data extraction forms and then into a computerized database. All computerized data will be double entered to verify accuracy of entry. Electronic data including all study databases and supporting electronic documentation will be archived to large-scale digital tape on a daily basis. On a monthly basis, a complete backup tape will be transported off-site to the Kampala Data Management Center (DMC) for rotating secure storage. In addition, the database from the backup will be placed onto one of the Kampala DMC servers as a data mirror for read-only access in the event that the Tororo web-site becomes temporary unavailable.

## 10.2 Data Quality Assurance and Monitoring

In order to insure data quality, the study Data Manager will perform a quarterly data quality audit. For this audit a 1% random sample of study forms entered into the data management system from the previous 2 weeks will be selected and compared for accuracy with the original case-report forms and source documents. In addition, the study the Data Manager will perform monthly reviews of the 100% double data entry data verification logs and the data management system audit trail log to identify potential data quality issues.

## 11.0 HUMAN SUBJECTS

### 11.1 Risks and Benefits

There are minimal direct benefits to the study subject for participation in the study. Free medical treatment for malaria is provided in Uganda. In Uganda, typical treatment for malaria involves the provision of medications, but no set schedule of follow-up after treatment. In our study, we will provide an increased level of care, primarily through enhanced follow-up of participants. However, we will not list this as a benefit on our informed consent documents. The risks have been reduced to a minimum. Participants will already be requiring AL for their malaria therapy. For children, we have consciously considered the guidelines set forth by the UCSF HRPP & IRB of 3ml/kg for blood sample collection and have optimized all assay requirements for accurate quantification of drug concentrations using the lowest amount of blood. We have also consulted other recommendations. The most conservative recommendations suggest no more than 2.5% (~2 mL/kg) of total blood volume within a 24 hour period or 5% (~4 mL/kg) within a 30 day period. The NIH guidelines state that no more than 3 mL/kg are to be drawn in a single blood draw (24 hour period) and no more than 9.5 mL/kg are to be drawn over any eight week period for the purposes of research in children. We feel it is unlikely the participant would be harmed by taking the amount of blood required in this study. For even children as small as 5 kg, the amount of blood that will be drawn in a 24 hour

period will not exceed 1.2 mL/kg. For the total amount collected over 42 days of follow-up the amount of blood that will be drawn will not exceed 5.3 mL/kg, which are well within these limits.

There is small chance of infection from performing blood draws. Additional risks include anxiety from HIV testing and learning of testing results. Participants will be counseled regarding test results and referred for medical care if necessary.

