## 6.9 Blood volumes

### **Intensive PK study**

The total blood volumes collected from intensive PK study participants during the 42-day follow-up period for single episode of malaria will be no more than 28 mL (~6 teaspoons). (Section 11.1).

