- 14 Additional 200uL capillary samples for RNA studies will be done on these days. RNA studies will not be done on participants under 10kg.

- 
- 15 Day 10 visit can be done in a subset of participants in either the clinic or by home visitor for collection of approximately 250uL for RNA and filter paper. Sampling will note will not be done on participants under 10kg.
  - 16 Total blood volume in either arm is between 5-6 teaspoons over 42-days of follow-up for scheduled visits
  - 17 Perform ECG on subgroup of participants. ECGs will be performed at baseline (before the administration of first dose), prior to and 4-6 hours post-last dose, Day 8, and Day 28. ECG will be performed on Day 3 for 3-day regimen and on Day 5 for 5-day regimen.

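### Section 11.1's claim that blood volumes are well inside all quoted limits fails for the limit of about 4 mL/kg per 30 days, and Appendix A omits part of the volume reduction for children under 10 kg

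*Combined protocol and SAP*

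**What the plan says.** Section 11.1 (Risks and Benefits) lists an institutional guideline "of 3ml/kg for blood sample collection", with no period attached. It then gives recommendations that it calls the most conservative: about 2 mL/kg in 24 hours and "5% (~4 mL/kg) within a 30 day period". Last come funder guidelines of 3 mL/kg in a single draw (24 hours) and "no more than 9.5 mL/kg are to be drawn over any eight week period".

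It then gives two figures for this study. The daily one takes a child of 5 kg as its example and says that the volume over such a "period will not exceed 1.2 mL/kg". The 42-day total "will not exceed 5.3 mL/kg, which are well within these limits".

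Elsewhere:

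- Section 4.1.1 sets a minimum entry weight of 6 kg.
- Section 6.9 says the intensive PK volume per 42-day episode "will be no more than 28 mL". Under its population PK heading, it says that neither RNA nor metabolomic studies are done in children under 10 kg.
- Appendix A gives approximate volumes per visit. Footnote 14 says "RNA studies will not be done on participants under 10kg", and footnote 15 bars the Day 10 sample below that weight. The 1 mL metabolomics and molecular draws on Days 0, 14, 28 and 42 carry no weight restriction.

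**The concern.** The 42-day figure of 5.3 mL/kg is above one of the limits listed in the same paragraph. Those windows differ (42 days against 30), so the question is how much of the volume falls inside 30 days.

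Section 11.1 is the protocol's justification of blood volume, and the protocol goes to four review bodies (Section 11.5). HIV-uninfected infants can enter from 6 months of age and 6 kg, with hemoglobin down to 7.0 g/dL, so the smallest children have the least margin. There is a practical side as well. Staff who work from the Appendix A schedule could take blood that Section 6.9 says is not taken from these children.

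**Working it through.** **Inputs.** Appendix A, 5-day arm, mL by study day: 5.6 (D0), 0.6 (D1), 0.6 (D2), 0.6 (D3), 0.6 (D4), 4.2 (D5), 0.4 (D6), 0.6 (D8), 0.3 (D10), 5.4 (D14), 0.6 (D21), 5.2 (D28), 0.4 (D35), 1.2 (D42). An unscheduled visit is 1.4 mL. The largest single day in either appendix is 5.8 mL (Appendix B, Day 0).

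**1. Reproduce the plan's figures.**

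- 42-day total: the sum is 26.3 mL, and 26.3 / 5 = 5.26, which rounds to 5.3 mL/kg. The 3-day arm gives 25.7 / 5 = 5.14.
- 24-hour figure: 5.8 / 5 = 1.16, which rounds to 1.2 mL/kg.

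Both reproduce at 5 kg, with all RNA and metabolomics draws included and unscheduled visits excluded.

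**2. Volume inside 30 days.** Days 0 to 28: 26.3 − 0.4 − 1.2 = 24.7 mL, which is 94% of the 42-day total.

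- At 5 kg: 24.7 / 5 = 4.94 mL/kg, about 24% above 4.
- At 6 kg: 24.7 / 6 = 4.12 mL/kg, about 3% above 4.
- 3-day arm: 24.1 mL, giving 4.82 and 4.02 mL/kg.
- Weight at which 24.7 mL equals 4 mL/kg: 24.7 / 4 = 6.2 kg.

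**3. Effect of the omission below 10 kg (5-day arm, 6 kg, Day 28).** RNA-related samples are 0.2 (D3) + 0.2 (D8) + 0.3 (D10) + 0.2 (D21) = 0.9 mL. Metabolomics and molecular draws are 1 mL on each of D0, D14 and D28, so 3.0 mL.

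| Basis | mL by Day 28 | mL/kg at 6 kg |
|---|---|---|
| Full schedule | 24.7 | 4.12 |
| RNA omitted (Appendix A footnotes) | 23.8 | 3.97 |
| RNA and metabolomics omitted (Section 6.9) | 20.8 | 3.47 |

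At 6 kg, 4 mL/kg is 24.0 mL, so the RNA-only basis leaves 0.2 mL. One unscheduled visit at 1.4 mL gives 25.2 / 6 = 4.20 mL/kg. At 5 kg, omitting both still gives 20.8 / 5 = 4.16 mL/kg, but a 5 kg child cannot enrol.

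**4. The cap in Section 6.9.** 28 / 5 = 5.60 and 28 / 6 = 4.67 mL/kg; neither is 5.3. The gap to the schedule is 28 − 26.3 = 1.7 mL, room for one unscheduled draw (26.3 + 1.4 = 27.7). The cap and the stated maximum therefore appear to count different things.

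**5. The other limits.** For one episode, 5.3 mL/kg is 56% of the eight-week 9.5 mL/kg. The daily 1.2 mL/kg is below both 24-hour limits (about 2, and 3).

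**The case against.** The strongest defence is that Section 11.1 ends its list with a single-draw limit and an eight-week limit, then gives a 24-hour and a 42-day figure. Paired that way, both figures are comfortably inside. The 5 kg example overstates exposure per kilogram, because 6 kg is the minimum. The omission sentence in Section 6.9 is worded generally and can be read as covering both studies; applied, a 6 kg child stays below 4 mL/kg on scheduled draws. The volumes and the 30-day limit are also all approximate.

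Much of this stands, and it rules out several stronger readings:

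- A reader might infer that 5.3 is a calculation error because 28 / 5 = 5.6. It is not; it follows from the scheduled visits.
- A reader might infer that eligible children will be bled beyond 4 mL/kg. The documents do not show this. With the Section 6.9 omission the figure is about 3.5, and even RNA omission alone gives 3.97 at 6 kg.
- A reader might infer that the 3 mL/kg guideline is broken throughout. No period is given, so this cannot be judged. Even read as a 42-day limit, the population 5-day schedule with both omissions is 17.6 / 6 = 2.9 mL/kg.

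What does not stand is the wording. The 30-day recommendation is one of the limits listed, the text claims compliance with the list, and no 30-day figure is given. Nor does the generous example help, since the claim fails on that example.

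**Conclusion.** The point holds as a defect in the safety statement and a gap between sections; no over-limit sampling of eligible children is demonstrated. On Section 11.1's own basis the 30-day volume is 4.94 mL/kg against a quoted limit of about 4. At the entry minimum it is 4.12 with full draws, and only children below about 6.2 kg are affected. With the Section 6.9 omission it is about 3.5.

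The part with practical weight is Appendix A: following its footnotes allows 3 mL more by Day 28 from a child under 10 kg than Section 6.9 intends, and leaves a 6 kg child 0.2 mL below the 30-day limit.

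The results assume the approximate per-visit volumes in Appendix A, scheduled visits only unless stated, and one malaria episode. The 3.5 figure also assumes that the Section 6.9 omission applies to the intensive study and removes the whole 1 mL draw. If some is kept for other molecular work, the figure lies between 3.47 and 3.97.

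**What to change.** Reconcile Sections 6.9 and 11.1 and Appendix A:

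- Carry the Section 6.9 omission of metabolomics blood below 10 kg into Appendix A's footnotes, beside the RNA omission.
- Restate Section 11.1 at 6 kg, with 24-hour, 30-day and 42-day totals for each study. Say whether unscheduled draws and the under-10 kg omission are counted, so that the stated maximum agrees with the 28 mL cap.
- Replace the general assurance with each figure set against the limit whose window matches it.
- State the period to which the 3 mL/kg guideline applies.

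The cost is an edit to one paragraph and some footnotes. No data are lost beyond draws that Section 6.9 already excludes.

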### **11.2 Treatment and Compensation for Injury**

If the participant is injured as a result of being in this study, treatment will be available through TDH and MGH. Makerere University, UCSF, Yale, and NICHD do not normally provide any other form of compensation for injury.

### **11.3 Costs to the Subjects**

There will be no cost to the participant or their parents/guardians/participants for participation in this study.

### **11.4 Reimbursement of Subjects**

Participants will not be paid for their participation in the study. We will provide all routine medical care, including evaluations, medications available in our clinic, and cost of any transportation free of charge. On certain days, participants will have to be in the clinic for several hours. On those days, we will provide food and drink to participants (breakfast, dinner, and/or snacks) to ensure their well-being. In addition, we will reimburse the cost of consultation for referrals made by study physicians to other clinics and services within TDH or MGH using available funds when available. However, reimbursement of all diagnostic tests and treatment recommended outside the study clinic cannot be guaranteed in all circumstances.

### **11.5 Institutional Review Board (IRB) Review and Informed Consent**

This protocol, all procedures and consent forms, and any subsequent modifications must be reviewed and approved by the IRBs of participating institutions in both the U.S. and in Uganda. This includes the UCSF Human Research Protection Program & Institutional Review Board (HRPP & IRB), the Yale Human Investigations Committee (HIC), the Makerere University School of Medicine Research Ethics Committee (SOMREC), and the Uganda National Council of Science and Technology (UNCST).

All consent forms will be translated into the local language (Jopadhola, Teso, Swahili, Luganda, Samia, and English) and back-translated into English to ensure correct use of language. Consent forms will be read aloud to parents by trained study interviewers. The informed consent will describe the purpose of the study, all the procedures involved, and the risks and benefits of participation. Interviewers will ask parents/guardians/participants to summarize the study and explain the reasons why they want to participate. Either a signature or a thumbprint (for parents/guardians who

cannot read) will be acceptable to confirm informed consent for participation in the study.

### **11.6 Study Discontinuation**

This study may be discontinued at any time by the NIH, respective IRBs or other Governmental agencies in the United States or Uganda as part of their duties to ensure that research subjects are protected

### **11.7 Definition of Parent/Guardianship**

For this project, we will define a parent as someone who attests that he/she is the biological parent of the potential participant. However, it has been found in Uganda that a high number of the HIV-infected children have lost one or both parents. These children live with caretakers who do not have documented formal guardianship status because there is no formal, legal guardian system in Uganda. In Uganda, orphan children are customarily cared for by one or more relatives; a single individual family member is not usually identified as the sole guardian or custodian of the child. We will define a guardian as someone who identifies him/herself as the primary caregiver who is able to make all health care decisions for the potential participant. A guardian must be at least 18 years of age, however; a parent may be less than 18 years of age. These definitions are currently approved for use in current research projects conducted in Uganda following extensive discussion with the Ugandan Ministry of Justice, the Uganda National Council of Science, the Makerere University College of Health Sciences, and the NIH in 2006.

## **12.0 PUBLICATION OF RESEARCH FINDINGS**

The findings from this study may be published in a medical journal. No individual identities will be used in any reports or publications resulting from the study. The researchers will publish results of the trial in accordance with NICHD, UNCST, UCSF, Yale, and Makerere University guidelines.

## **13.0 BIOHAZARD CONTAINMENT**

As the transmission of HIV and other blood-borne pathogens can occur through contact with contaminated needles, blood, and blood products, appropriate blood and secretion precautions will be employed by all personnel involved in the drawing of blood, exposure to blood and secretions, and shipping and handling of all specimens for this study. We will follow the current guidelines set forth by the Centers for Disease Control and Prevention and the NIH. All infectious specimens will be transported using packaging mandated in the Federal Code of Regulations, CDC 42 CFR Part 72.

## APPENDIX A. SCHEDULE OF EVALUATIONS: INTENSIVE PK STUDY

INTENSIVE PK STUDY															
Study Day	0 	1	2	3	4	5 	6 	8 	10 	14	21	28	35	42	Any other day 
ADMINISTRATIVE AND REGULATORY PROCEDURES															
Screening and study participation informed consent	X														
HIV counseling and referral if necessary 	X														
Collect locator information	X														
CLINICAL AND LABORATORY EVALUATIONS															
History 	X	X	X	X	X	X 	X 	X		X	X	X	X	X	X
Physical Examination 	X	X	X	X	X	X 	X 	X		X	X	X	X	X	X
HIV testing and documentation 	X														
Hematology and Chemistries 	4mL									4mL		4mL			
Rapid Diagnostic Test (RDT)	X							X		X	X	X	X	X	X
Thick Blood Smear  and Filter Paper collection (finger stick) for LAMP	X	X	X	X	X	X 	X 	X	X	X	X	X	X	X	X
Thin Blood Smear 	X														X
Electrocardiogram (ECG) 	X			X		X		X				X			
DRUG ADMINISTRATION															
AL dosing for all study subjects 	X	X	X	X	X 	X 									
Antiretroviral dosing for HIV-infected subjects 	X	X	X	X	X	X	X	X		X					
INTENSIVE PHARMACOKINETIC STUDY SAMPLING (VENOUS OR CAPILLARY DRAWS AS PER SECTION 6.7)															
3-day AL regimen Artemether and Lumefantrine	200µL (pre-AL) 2 and 4 hrs post-dose	200µL 2 and 4 hrs post-dose	200µL 2 and 4 hrs post-dose	500 µL (0, 0.5, 1, 2  , 3, 4, 6 and 8  hrs)  (additional 200 µL at 2 and 8 hrs)	200µL (24 hrs)			200µL (120 hrs)		200µL (288 hrs)	200µL (456 hrs)				200µL

5-day AL regimen Artemether and Lumefantrine 	200µL (pre-AL) 2 and 4 hrs post- dose	200µL 2 and 4 hrs post- dose	200µL 2 and 4 hrs post- dose	200µL 2 and 4 hrs post- dose	200µL 2 and 4 hrs post- dose	500 µL (0, 0.5, 1, 2, 3, 4, 6 and 8 hrs)	200µL (24 hrs)	200µL (120 hrs)		200µL (288 hrs)	200µL (456 hrs)				200µL
Blood for metabolomics and molecular studies	1mL			X 				X 	X 	1mL	X 	1mL	X 	1mL	1mL
APPROXIMATE TOTAL BLOOD VOLUME (mL)	5.6	0.6	0.6	0.6-4.8	0.4-0.6	0.2-4.2	0.4	0.6	0.3	5.4	0.6	5.2	0.4	1.2	1.4

### Explanation of Intensive PK schedule of events (Appendix A):

- 1 As is standard practice, study Day 0 stipulates the time of diagnosis of uncomplicated malaria and initiation of AL treatment.
- 2 Rapid HIV test will be performed to determine eligibility to enroll as either HIV infected or HIV uninfected participant, although children must be stabilized on EFV-based ART for 10 days prior to enrollment. Positive HIV test results to be confirmed by Western Blot or HIV RNA after enrollment.
- 3 History will include general medical history, diagnosis, medication (including ingestion of herbs), allergies, and current symptoms.
- 4 Physical examination will include weight, height, and vital signs (temperature, pulse, blood pressure, respiratory rate), lymphadenopathy, hepatomegaly, splenomegaly, infections in ears, mouth, pharynx or skin and pulmonary, cardiac, neurologic or skeletal abnormalities and anthropometric assessments. Mid-upper arm circumference will also be collected at time of first enrollment for each episode of malaria.
- 5 Hematology/chemistry draws entail a 4mL venous sample for CBC, differential, ALT/AST, and creatinine. AST is incorporated as part of chemistries at all blood draws.
- 6 A thin smear is performed to assist in species identification.
- 7 Dosing of AL for all subjects undergoing intensive PK sampling will be scheduled to assure the last dose of a six or 10 dose regimen is given in the morning (Day 3 or 5).
- 8 On stable ART as per clinical management in TDH or MGH or other referral clinic; ART dosing permitted at home, but time of administration is recorded
- 9 For subjects participating in intensive PK evaluations, sampling for the 120 PK sample will occur on Day 8 since these subjects receive the 6th or 10th AL dose on Day 3 or 5.
- 10 Patients presenting on an unscheduled day for a sick visit will undergo sampling for lumefantrine PK if found to have a positive malaria thick
- 11 Specifically, for children receiving 5-day AL
- 12 At 2 and 8 hours an additional 200µL will be drawn via a capillary stick to permit correlation of venous and capillary concentrations for the artemisinins.
- 13 At approximately 0, 24, 48, and 72, 84 and 96 hours post the first dose of AL or until blood smears are consistently negative. In a subset of participants, additional thick blood smears will be done on the days of AL doses to assess parasite clearance.
- 14 Additional 200uL capillary samples for RNA studies will be done on these days. RNA studies will not be done on participants under 10kg.

- 
- 15 Day 10 visit can be done in a subset of participants in either the clinic or by home visitor for collection of approximately 250uL for RNA and filter paper. Sampling will note will not be done on participants under 10kg.
  - 16 Total blood volume in either arm is between 5-6 teaspoons over 42-days of follow-up for scheduled visits
  - 17 Perform ECG on subgroup of participants. ECGs will be performed at baseline (before the administration of first dose), prior to and 4-6 hours post-last dose, Day 8, and Day 28. ECG will be performed on Day 3 for 3-day regimen and on Day 5 for 5-day regimen.

## APPENDIX B. SCHEDULE OF EVALUATIONS: POPULATION PK STUDY

POPULATION PK STUDY														
Study Day	0 	1	2	3	4	5	7 	10 	14	21	28	35	42	Any other day 
ADMINISTRATIVE AND REGULATORY PROCEDURES														
Screening and study participation informed consent	X													
HIV counseling and referral if necessary 	X													
Collect locator information	X													
CLINICAL AND LABORATORY EVALUATIONS														
History 	X	X	X	X	X	X	X		X	X	X	X	X	X
Physical Examination 	X	X	X	X	X	X	X		X	X	X	X	X	X
HIV testing and documentation 	X													
Hematology and Chemistries 	4mL								4mL		4mL			
Rapid Diagnostic Test (RDT)	X						X		X	X	X	X	X	X
Thick Blood Smear  and Filter Paper collection (finger stick) for LAMP	X	X	X	X	X	X	X	X	X	X	X	X	X	X
Thin Blood Smear 	X													X
Electrocardiogram (ECG) 	X			X		X	X				X			
DRUG ADMINISTRATION														
AL dosing for all study subjects 	X	X	X	X 	X 									
Antiretroviral dosing for HIV- infected subjects 	X	X	X	X	X	X	X		X					
INTENSIVE PHARMACOKINETIC STUDY SAMPLING (VENOUS OR CAPILLARY DRAWS AS PER SECTION 6.7)														
3-day AL regimen Artemether and Lumefantrine	200µL (pre-AL, 2 and 4 hrs post-dose)	200µL 2 and 4 hrs post- dose	200µL Pre-dose  , 2 and 4 hrs post-dose	200µL (24 hrs)			200µL (120 hrs)		200µL (288 hrs)	200µL (456 hrs)				200µL
5-day AL regimen Artemether and Lumefantrine 	200µL (pre-AL, 2 and 4 hrs post-dose)	200µL 2 and 4 hrs post- dose	200µL 2 and 4 hrs post-dose	200µL  2 and 4 hrs post- dose	200µL  Pre- dose  , 2 and 4 hrs post- dose	200µL  (24 hrs)	200µL (120 hrs)		200µL (288 hrs)	200µL (456 hrs)				200µL
Blood for metabolomics and molecular studies	1mL			X 			X 	X 	1mL	X 	1mL	X 	1mL	1mL
APPROXIMATE TOTAL BLOOD VOLUME (mL)	5.8	0.6	0.8	0.4-0.8	0.2-0.6	0.4	0.6	0.3	5.4	0.6	5.2	0.4	1.2	1.4

---

## Explanation of Population PK schedule of events (Appendix B):

- 1 As is standard practice, study Day 0 stipulates the time of diagnosis of uncomplicated malaria and initiation of AL treatment.
- 2 Rapid HIV test will be performed to determine eligibility to enroll as either HIV infected or HIV uninfected participant, although children must be stabilized on EFV-based ART for 10 days prior to enrollment. Positive HIV test results to be confirmed by Western Blot or HIV RNA after enrollment.
- 3 History will include general medical history, diagnosis, medication (including ingestion of herbs), allergies, and current symptoms.
- 4 Physical examination will include weight, height, and vital signs (temperature, pulse, blood pressure, respiratory rate), lymphadenopathy, hepatomegaly, splenomegaly, infections in ears, mouth, pharynx or skin and pulmonary, cardiac, neurologic or skeletal abnormalities and anthropometric assessments. Mid-upper arm circumference will also be collected at time of first enrollment for each episode of malaria.
- 5 Hematology/chemistry draws entail a 4mL venous sample for CBC, differential, ALT/AST, and creatinine. AST is incorporated as part of chemistries at all blood draws.
- 6 A thin smear is performed to assist in species identification.
- 7 Dosing of AL for all subjects will not be adjusted as done for intensive study so the last dose will occur in the evening of Day 2 (3 day AL) or 4 (5 day AL)..
- 8 On stable ART as per clinical management in TDH or MGH or other referral clinic; ART dosing permitted at home, but time of administration is recorded
- 9 For subjects participating in population PK evaluations, sampling for the 120 PK sample will occur on Day 7 since these subjects will not have adjustments in their dosing
- 10 Patients presenting on an unscheduled day for a sick visit will undergo sampling for lumefantrine PK if found to have a positive malaria thick
- 11 Specifically, for children receiving 5-day AL
- 12 At approximately 0, 24, 48, and 72, 84 and 96 hours post the first dose of AL or until blood smears are consistently negative. In a subset of participants, additional thick blood smears will be done on the days of AL doses to assess parasite clearance.
- 13 Additional 200uL capillary samples for RNA studies will be done on these days. RNA studies will not be done on participants under 10kg.
- 14 Day 10 visit can be done in a subset of participants in either the clinic or by home visitor for collection of approximately 250uL for RNA and filter paper. Sampling will not be done on participants under 10kg.
- 15 Total blood volume in either arm is between 4-5 teaspoons over 42-days of follow-up for scheduled visits
- 16 Perform ECG on subgroup of participants. ECGs will be performed at baseline (before the administration of first dose), the next morning following the last dose, Day 7, and Day 28. ECG will be performed on Day 3 for 3-day regimen and on Day 5 for 5-day regimen.
- 17 A 200ul capillary draw will be done pre-dose on Day 2 in the 3-Day regimen and on Day 4 in the 5-Day regimen, in a subset of children, to look at AL drug level. This will inform the study team of drug adherence.

